8.4.1 Patient diaries

Upon providing informed consent, each patient will be given a study diary and provided guidance in its use. There will be 2 diaries, the first one will cover 4 weeks of baseline data (between visits 1 and 2) and the second one will cover the 4 weeks prior to each physician visit (visits 3 to 6). At the visit following completion of the diary, the patient will return his/her diary and will be given a new one. Data from the diary will be entered into the eCRF. The diary will be kept in the source files at the investigational site.

The 4-week diaries will include sections for information such as:

- Insulin dose and time of administration
- Details of missed doses and dose-time flexibility
- Number of SMBG test strips used
- Information related to hypoglycaemic episodes. Each time the patient has a symptom of hypoglycaemia or his/her blood sugar level is below or equal to 3.9 mmol/L (70 mg/dL), the patients will be encouraged to complete the diary (exact time, PG value, assistance required or not)
- Resource use due to hypoglycaemia.

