8.4.2 Visit procedures

The physician must keep a patient enrolment log and a log of patients evaluated for but not included in the study throughout the enrolment period. These can be combined in one document.

A sequence of patient numbers will be assigned to each study site. All patients entering the baseline period will receive a patient number that will be used to identify the patient throughout the study. Patients withdrawn from the study retain their patient number, if already given. New patients must always be allocated a new patient number.

Patients who are enrolled in the study will be provided with contact address(es) and telephone number(s) of the physician site and/or staff.

Patients will be asked about any AEs during each visit by the physician or study site staff. This may be done by posing a simple question such as “have you experienced any problems since the last visit?” However, only SADR, MESI, pregnancies and severe hypoglycaemic events (regardless of seriousness or causality) will be collected in this study as specified in Section [10](#).

In case a patient is being prematurely withdrawn from the study the physician will ensure that the procedures for the last visit are recorded, if possible. The primary reason (adverse reaction or other) for discontinuation must be specified in the eCRF.

The study consists of a 4-week baseline period followed by a 12-month (± 45 days) observation period. All visit dates are based on the date the patient started Tresiba[®] medication (Month 0, visit 2). The time window for visits 3, 4, 5, and 6 (Months 3, 6, 9 and 12) is ± 45 days. Visits are not protocol defined but based on the estimated regularity of visits to a treating physician under normal clinical practice. It is not expected that all patients will attend all visits.

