8.4.3 Visit 1 Physician plans to initiate Tresiba[®] (Week -4)

The patient will receive complete information about the study both orally and in writing. Informed consent must be given prior to any trial-related data being collected.

The visit will include:

- Signature of informed consent and recording of the date informed consent was given
- Determination of eligibility by checking the inclusion/exclusion criteria (Section [8.2.2](#) and Section [8.2.3](#)). The decision as to which T1DM and T2DM patients will start Tresiba[®] treatment is determined by the treating physician
- Distribution of all PROs to be completed by the patient. This will be done prior to any following steps. The questionnaires will be administered while the subject is in the waiting room or another dedicated room
- Demography – collecting age, sex, ethnicity
- Blood pressure (systolic and diastolic) and height measurements, if available
- Body weight (kg), if available
- Medical history
- Physician will document if the patient is hypo-prone
- Concomitant medications (related to diabetes - including insulin dosing regimen)
- Physician will document if the patient is a high dose insulin user (>80 U/day)
- Collection of the most recent HbA1c and FPG and date of the measurements
- Patients will be interviewed and asked to recall any severe hypoglycaemic episodes in the 6 months prior to this visit
- Distribution of diary and guidance on use.

The patient will be instructed to:

- Continue on current therapy, as prescribed by the physician and lifestyle interventions
- Record in the diary every episode of hypoglycaemia occurring over the following 4 weeks
- Record in the diary insulin dose, time, and date (over the following 4 weeks)
- Record in the diary if any doses are missed and what the patient did
- Record in the diary how many SMBG strips they use over the following 4 weeks
- Record in the diary any resource use due to hypoglycaemia over the following 4 weeks
- Bring the diary to the next clinical visit.

An appointment will be made for their next usual clinical visit (visit 2, initiation) in approximately 4 weeks (+14 days).

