8.4.4 Visit 2, Initiation/Baseline (Month 0)

The decision to treat patients is entirely based on the physician's decision in accordance with local practice.

This visit will include:

- Check of inclusion, exclusion and withdrawal criteria (see Sections [8.2.2](#), [8.2.3](#) and [8.2.4](#))
- Distribution of all PRO questionnaires to be completed by the patient. This will be done prior to any following steps
- Body weight (kg), if available
- Concomitant medications, including current insulin dosing regimen, will be recorded
- Collection of the most recent HbA1c and FPG and date of the measurements
- Collection of safety information. Patients will be asked about any AEs as part of standard care. Each SADR, severe hypoglycaemic episode (regardless of physician's evaluation of seriousness and causality), MESI, and pregnancies will be recorded on a separate AE form and SIF according to existing reporting procedures and timelines
- Collection of diary and distribution of a new one
- The patient will be asked what their total daily dose of bolus insulin was on the day prior to the visit, if applicable
- The patient will be asked if their insulin treatment required them to change any social, leisure, and working time activities
- Physician will document the reason for switching or not switching to Tresiba[®] treatment as applicable
- Based on physician decision, patients will commence treatment on Tresiba[®]

The patient will be instructed to:

- Continue on current therapy including Tresiba[®], as prescribed by the physician and lifestyle interventions
- Record in the diary every episode of hypoglycaemia occurring over the 4 weeks prior to the next visit
- Record in the diary insulin dose, time, and date (for 4 weeks prior to the next visit)
- Record in the diary if any doses are missed and what the patient did, and details of dose-time flexibility
- Record in the diary how many SMBG strips they used over the 4 weeks prior to the next visit
- Record in the diary any resource use due to hypoglycaemia over the 4 weeks prior to the next visit
- Bring the diary to the next clinical visit.

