8.4.5 Observation period (standard routine visits)

The time window for visits 3, 4, 5, and 6 (Months 3, 6, 9, and 12) are ± 45 days. Visits are based on the regularity of visits to a treating physician under normal clinical management of a diabetic patient.

These visits will include:

- Patients will be assessed to determine if they meet any of the withdrawal criteria (Section [8.2.4](#)).
- Distribution of all PRO questionnaires to be completed by the patient. This will be done prior to any following steps. The questionnaires will be administered while the subject is in the waiting room or another dedicated room.
- Body weight (kg), if available.
- Collection of the most recent HbA1c and FPG and date of the measurements.
- The patient will be asked what their total daily dose of bolus insulin was on the day prior to the visit, if applicable.
- The patient will be asked if their insulin treatment required them to change any social, leisure, and working time activities.
- Concomitant medications, including current insulin dosing regimen, will be recorded
- Collection of safety information. Patients will be asked about any AEs as part of standard care. Each SADR, severe hypoglycaemic episode (regardless of physician's evaluation of seriousness and causality), MESI, and pregnancies will be recorded on a separate AE form and SIF according to existing reporting procedures and timelines.
- Collection of diary (at all visits) and distribution of a new one at visits 3, 4 and 5 only.

- Patients will be asked their preference for Tresiba[®] or their previous treatment.

The patient will be instructed to (except for the end of study visit 6, Month 12):

- Continue on current therapy including Tresiba[®], as prescribed by the physician and lifestyle interventions
- Record in the diary every episode of hypoglycaemia occurring over the 4 weeks prior to the next visit
- Record in the diary insulin dose, time, and date (for 4 weeks prior to the next visit)
- Record in the diary if any doses are missed and what the patient did, and details of dose-time flexibility
- Record in the diary how many SMBG strips they used over the 4 weeks prior to the next visit
- Record in the diary any resource use due to hypoglycaemia over the 4 weeks prior to the next visit
- Bring the diary to the next clinical visit.

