8.9 Limitations of the research methods

The enrolled patients in the current non-interventional study are acting as their own control. Thus, the baseline period of 4 weeks prior to planned initiation of Tresiba[®] is crucial in order to obtain reference data for the enrolled patients. The baseline period also constitutes an evaluation period for the physician, in order to aid in the final decision whether to initiate Tresiba[®]. While no causal

relationships can be concluded based on a non-interventional study design, the aim is to explore the associations between Tresiba[®] and other anti-diabetic treatment regimens with regard to any hypoglycaemic episodes.

The absence of a comparator group results in a number of threats to internal validity of the study design, the most critical of which is that the design will not provide the ability to rule out many alternative explanations for changes from baseline.

Whilst this is a study of real world clinical practice, enhanced glucose monitoring during the 4-week baseline period may potentially bias the physician's decision to commence Tresiba[®] treatment. More frequent blood glucose monitoring and maintaining a diary is an important factor in improved blood glucose control. Based on the enhanced monitoring and hypoglycaemic episode data collected during the 4-week baseline period, patients who the physician considered candidates for a treatment switch to Tresiba[®] at visit 1, may have improved blood glucose control and, at visit 2, may no longer be considered candidates for switching treatment.

Furthermore, due to data collection procedures conducted at visit 1 (see [Table 8-1](#)), it is possible that treating physicians may selectively enrol only those patients deemed, by past medical history, to be less likely to experience a hypoglycaemic episode during the 4-week baseline period before switching to Tresiba[®]. This differential selection of patients introduces a form of systematic selection bias that will result in an underestimation of the true rate of hypoglycaemia among all T1DM and T2DM patients switched to Tresiba[®]. The impact of this type of selection bias is that rates obtained from this study population will represent only those patients with an a priori lower rate of hypoglycaemia.

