If treating physicians do not selectively enrol patients based on knowledge of past medical history, it is still likely that if a patient experiences a severe episode of hypoglycaemia during the 4-week baseline period, the treating physician may elect to switch them immediately to Tresiba[®] (or another product), making that patient ineligible to continue in this study. If this type of patient selection occurs systematically, then the study population will consist predominantly of patients with a history of non-severe hypoglycaemia, which will result in an underestimation of the true rate of hypoglycaemia among all T1DM and T2DM patients switched to Tresiba[®]. This could affect estimation of the change from baseline in hypoglycaemia rate as the baseline measure could be underestimated, thus making it harder (*ceteris paribus*) to get a large effect after Tresiba[®] (ie, a large change from baseline).

Once patients have entered the observation period it is not anticipated that the physician's perception and understanding of a patient by the detailed collection of hypoglycaemic episode data will influence the physician's decision to continue Tresiba[®] treatment.

The inclusion criteria have been made deliberately broad to reflect the real world diabetic population. However, the use of diaries and questionnaires in this study may bias data towards those patients, either through socio-economic or educational reasons, better able to monitor and maintain a diary and thus maintain improved blood glucose. It is anticipated that the broad inclusion criteria will provide data from a sufficiently wide demographic and thus reduce the impact of this bias.

Laboratory measurements will be performed locally as per standard clinical practice, results are therefore expected to show greater variability than if performed centrally.

Recall of event or dosage information is frequently associated with either high numbers of errors of missing values/fields in collected data. The use of a prospective diary will limit collection of erroneous or missing data.

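### Follow-up diaries are started by the patient, counting back from a visit with no fixed date, while the baseline diary starts at once. Capture of non-severe episodes may therefore differ before and after the switch.

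*Protocol*

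**What the plan says.** **Baseline.** Under Protocol 8.4.3 the patient receives the diary at visit 1 with guidance and is told: "Record in the diary every episode of hypoglycaemia occurring over the following 4 weeks". Visit 2 is booked at the same contact, about 4 weeks ahead with up to 14 days' leeway.

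**Follow-up.** At visit 2 (8.4.4), and with the same wording at visits 3 to 5 (8.4.5), a new diary is handed out with the instruction: "Record in the diary every episode of hypoglycaemia occurring over the 4 weeks prior to the next visit". On the timing of those visits, 8.4.2 says: "Visits are not protocol defined but based on the estimated regularity of visits to a treating physician under normal clinical practice". Section 8.4.5 adds: "The time window for visits 3, 4, 5, and 6 (Months 3, 6, 9, and 12) are ± 45 days". Section 8.4.2 also does not expect every patient to attend every visit. The procedures listed for visits 2 to 5 contain no booking step, no diary start date and no reminder.

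**Role in the analysis.** These diaries are the source of the primary endpoint (7.3.1, 8.3.1). Each patient serves as his or her own reference (8.1.1), and 8.9 acknowledges that there is no comparator group.

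**Acknowledgement.** Section 8.9 says of diary quality: "The use of a prospective diary will limit collection of erroneous or missing data". It does not mention that the baseline and follow-up diaries start differently. The checklist in Annex 2 answers No on whether the protocol addresses information biases (item 7.1.2).

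**The concern.** An uncontrolled before/after comparison of rates needs episodes to be captured equally well on both sides. Here the baseline period runs forward from a supervised start. A follow-up period runs backward from a date that the patient must already know 28 days ahead, using a diary handed out weeks earlier. If the visit is brought forward, or the start is forgotten, the diary is partial or is completed from memory. It is then no longer the prospective record that 8.9 relies on.

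The episodes most at risk are the non-severe ones. Under 8.3.2.1 these include symptom-free glucose readings at or below 3.9 mmol/L, and all of them count towards the primary endpoint. With no comparator, poorer capture after the switch has the same sign as a treatment benefit. No later analysis can recover a non-severe episode that was never written down.

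**Working it through.** **1. The plan's own figure.** Inputs from 8.5: mean paired difference 1 episode/PYE, SD 7, α = 0.05 (two-sided per 8.7.2.2), power 90%, withdrawal 15%. A paired t-test with the noncentral t distribution gives n = 517 (power 0.9001); the normal approximation gives 515. Then 517/(1 − 0.15) = 608.2. The stated 517 and 608 are reproduced.

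**2. The planned effect in diary terms.** One 28-day diary is 28/365.25 = 0.0767 PYE, and four follow-up diaries are 0.307 PYE. An effect of 1 episode/PYE is therefore about 0.31 episodes per patient over all four follow-up diaries.

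**3. Wait between receiving a diary and starting it.** At baseline it is 0 days. For visit 3, taking month 3 as 91 days, it is 91 − 28 = 63 days. Across the window it runs from (91 − 45) − 28 = 18 to (91 + 45) − 28 = 108 days. This measures the opportunity for error, not error itself.

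**4. Under-recording that would equal the planned effect.** Let R be the true rate, unchanged by the switch, and u the share of follow-up episodes not recorded relative to baseline, with all 28 days still counted as exposure. The spurious fall is R × u. Setting R × u = 1 gives u = 1/R. R is not in the protocol, so the values below are assumptions.

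| Assumed R (episodes/PYE) | u giving a fall of 1/PYE | Equivalent late start, 28 × u |
|---|---|---|
| 5 | 20% | 5.6 days |
| 10 | 10% | 2.8 days |
| 20 | 5% | 1.4 days |

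**5. Chance of a false significant fall.** Take no true change, n = 517, every follow-up diary started 3 days late and 28 days still counted. The spurious fall is R × 3/28: 0.54 at R = 5 and 1.39 at R = 13. One episode in a single diary is worth 1/0.0767 = 13 episodes/PYE, so SDs above the protocol's 7 are shown as well; those are assumptions.

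| SD | R = 5 | R = 13 |
|---|---|---|
| 7 (protocol) | 41% | 99.5% |
| 14 | 14% | 62% |
| 28 | 7% | 20% |

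The result depends strongly on R, on the SD and on the exposure rule. If only days actually covered by the diary count as exposure, a uniformly late start causes no bias in the rate. Forgotten or poorly recalled episodes still do.

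**The case against.** The strongest reply is that under-recording is a possibility which nothing in the protocol demonstrates, and that several safeguards exist.

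- **Dated doses.** Under 8.3.2.5 the time, amount and date of each Tresiba dose over the 4 weeks before a visit go from the patient's record into the eCRF, so a short diary will often be detectable. This stands in part: dated doses do not show that the hypoglycaemia pages were kept over the same days.
- **Severe episodes.** They are also collected as safety information at each visit and reported on separate forms (8.3.1, 8.4.5). This stands, and it limits the point to non-severe episodes.
- **Exposure and missing-diary rules.** They may be in the SAP, which is not at hand, and their absence is no finding. What remains is that such rules need the covered days and return status to be recorded.
- **Patient materials.** The diary itself is not shown and may carry a prompt. Visits do have nominal months, and sites may book ahead. This stands as a reason for restraint.
- **General caveat.** Section 8.9 concedes that other explanations for a change from baseline cannot be excluded. It does not name this one.

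Two stronger readings are tempting but unsupported. A reader might infer that losses occur only on the Tresiba side. Baseline diaries are also completed by patients and can be incomplete, and if some patients open a follow-up diary only when an episode occurs, with exposure counted from that entry, the bias could reverse. A reader might also infer from the reference in 8.9 to "enhanced glucose monitoring during the 4-week baseline period" that extra testing must add baseline episodes. But 8.3.2.6 asks for no self-measurement beyond clinical practice, 8.1.1 cites advice for close monitoring during the transfer and the following weeks, and 8.9 says that monitoring improves control, which could lower the baseline count.

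**Conclusion.** The two sides of the primary comparison are collected under different starting conditions, and 8.9 does not say so. That much is fixed by the text. Whether it biases the result, and by how much, cannot be determined from the protocol. At an assumed rate of 10 episodes/PYE with full 28-day exposure, 10% lower capture after the switch would match the planned effect. The required share is 20% at a rate of 5 and 5% at a rate of 20. A bias towards an apparent benefit is the more likely direction but not a certain one, and it concerns mainly non-severe episodes. This is a worthwhile, low-cost correction of a stated procedure. It is neither a contradiction nor a computational error, and the sample size is unaffected.

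**What to change.** - **Amend 8.4.4 and 8.4.5.** At visits 2 to 5 the site writes a calendar start date for the next 28-day diary on its cover. The diary runs from that date even if the visit moves.
- **Add eCRF fields for every diary, baseline included:** first and last day of hypoglycaemia recording, whether the diary was returned, and a confirmation when no episode occurred. Exposure can then be the days actually covered, and an unreturned diary is not read as zero episodes.
- **Amend 8.9.** Name the different start of the baseline and follow-up diaries as a possible information bias.
- **Report test strips per diary day** beside the primary rate for baseline and each follow-up diary. Strip counts are already collected (8.3.2.6).

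The cost is a short amendment, a date on the diary and a few eCRF fields. No visits are added and no clinical management changes. The drawback is that some diaries will end before the visit at which they are returned.

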8.4.5 Observation period (standard routine visits)

The time window for visits 3, 4, 5, and 6 (Months 3, 6, 9, and 12) are ± 45 days. Visits are based on the regularity of visits to a treating physician under normal clinical management of a diabetic patient.

These visits will include:

- Patients will be assessed to determine if they meet any of the withdrawal criteria (Section [8.2.4](#)).
- Distribution of all PRO questionnaires to be completed by the patient. This will be done prior to any following steps. The questionnaires will be administered while the subject is in the waiting room or another dedicated room.
- Body weight (kg), if available.
- Collection of the most recent HbA1c and FPG and date of the measurements.
- The patient will be asked what their total daily dose of bolus insulin was on the day prior to the visit, if applicable.
- The patient will be asked if their insulin treatment required them to change any social, leisure, and working time activities.
- Concomitant medications, including current insulin dosing regimen, will be recorded
- Collection of safety information. Patients will be asked about any AEs as part of standard care. Each SADR, severe hypoglycaemic episode (regardless of physician's evaluation of seriousness and causality), MESI, and pregnancies will be recorded on a separate AE form and SIF according to existing reporting procedures and timelines.
- Collection of diary (at all visits) and distribution of a new one at visits 3, 4 and 5 only.

- Patients will be asked their preference for Tresiba[®] or their previous treatment.

The patient will be instructed to (except for the end of study visit 6, Month 12):

- Continue on current therapy including Tresiba[®], as prescribed by the physician and lifestyle interventions
- Record in the diary every episode of hypoglycaemia occurring over the 4 weeks prior to the next visit
- Record in the diary insulin dose, time, and date (for 4 weeks prior to the next visit)
- Record in the diary if any doses are missed and what the patient did, and details of dose-time flexibility
- Record in the diary how many SMBG strips they used over the 4 weeks prior to the next visit
- Record in the diary any resource use due to hypoglycaemia over the 4 weeks prior to the next visit
- Bring the diary to the next clinical visit.

